16.2 Statistical analysis

16.2.1 Criteria for evaluation

All enrolled patients receiving at least one day of trial treatment will be included in the intent-to-treat (ITT) population. Patients who withdrew their consent will be excluded in the ITT population. The per-protocol population will include all patients from the ITT population except those who did not fulfil the inclusion criteria or discontinued trial treatment without virologic failure or adverse event as judged by the DSMB as related to trial treatment or procedure.

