9.2 Secondary Endpoints

Biological efficacy

- Percentage of patients remaining in therapeutic success up to week 48 and week 96 defined as the absence of virological failure and the absence of treatment interruption due to adverse event judged by DSMB as related to the trial treatment or procedure
- Percentage of patients in virological success (plasma HIV-RNA \leq 50 copies/mL) up to week 96
- Percentage of patients with trial treatment interruption
- Percentage of patients with plasma HIV-RNA VL between 51 and 200 copies/mL and percentage of patients with plasma HIVRNA VL > 200 copies/mL at time of virological failure
- Median time of virological failure (time limit between the date of the study treatment initiation and the date of virological failure)
- Percentage of patients with RAL and/or ETR resistance mutations in case of virological failure and percentage of patients with resistant viruses to all study drug's class in case of virological failure
- Factors associated with the occurrence of plasma HIV-RNA VL > 50 copies/mL (genotype history, pre-cART VL, plasma drug concentration (etravirine, raltegravir) at the virological rebound, viral reservoir measured by HIV-DNA at D0 and adherence assessed with a self-questionnaire)
- Evolution of total cell-associated HIV-DNA from D0 to W48 and W96
- Evolution of CD4+, CD8+ T cells counts and CD4/CD8 ratio at each time point from D0

Tolerability and Metabolic Impact

- Percentage of patients with at least one serious adverse event as judged by DSMB as related to the trial treatment or to the trial strategy
- Percentage of patients with grade 3 or grade 4 clinical and biological adverse events
- Evolution of metabolic parameters (fasting triglycerides, total cholesterol, HDL-cholesterol, LDL-cholesterol and fasting glycemia)
- Evolution of the calibrated Framingham risk score and of the SCORE risk equation including HDL cholesterol (from the European Cardiovascular Society) from D0 to W48 and W96
- Evolution of renal function measured using proteinuria and the CKD-EPI (Chronic Kidney Disease Epidemiology Collaboration Calculator) formula to estimate the Glomerular Filtration Rate (GFR) from D0 to W96
- Evolution of limb lean, limb fat, visceral adipose tissue (VAT) and subcutaneous adipose tissue (SAT), measured by DXA scan (Dual-energy X-Ray Absorptiometry), from D0 to W48 and W96 (DXA scan sub-study, 80 patients)

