11.9.1 Consent withdrawal

In case of a withdrawal of the consent, the investigator must inform the CMG UMR S 1136 to have the procedure to follow. The patient's data will be removed (from the date of the consent's withdrawal) from the database according to the law (loi n°78-17 du 6 janvier 1978 modifiée, article 38) and the biological samples will be destroyed.

Any consent withdrawal has to be confirmed to the Methodology Centre by using the dedicated form in the eCRF within the two working days, and date of withdrawal.

Subjects withdrawing from the trial may be replaced if considered necessary by the Coordinating investigator.

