16.2.2 Statistical methods

The primary endpoint is the virological success up to week 48 defined by the absence of 2 consecutive HIV-RNA plasma VL > 50 copies/mL within 2 to 4 weeks.

The therapeutic success is defined by the absence of virological failure and the absence of treatment interruption due to adverse event judged by DSMB as related to the trial treatment or procedure up to week 96.

In particular:

- Patients with 2 or more consecutive missing HIV-1 RNA plasma viral load values or lost to follow up will be considered as patients with treatment failure (failing patients).
- Patients who discontinue the treatment due to adverse event judged by DSMB as related to the trial treatment or procedure will be considered as failing patients.
- Patients who discontinued the treatment due to adverse event judged by DSMB as NOT related to the trial treatment or procedure will not be considered as failing patients.
- Patients who gave up will not be considered as failing patients.
- Patients who discontinued the trial treatment for any reason other than a virological failure or adverse event judged by DSMB as related to the trial treatment will not be considered as failing patients.
- Patients with a missing HIV-1 RNA value between 2 documented HIV-1 RNA plasma viral loads \leq 50 copies/mL will not be considered as failing patients.

Analysis of the primary endpoint will be performed on both ITT and per protocol populations. The 95% two-sided confidence interval of the percentage of patients in therapeutic success will be calculated and raltegravir/etravirine will be considered as an acceptable strategy if the lower bound is greater than 90%.

The changes in continuous endpoints will be compared in the ITT population (LOCF or other imputation method to be defined in the statistical analysis plan) using a two-sided non-parametric paired Wilcoxon test with a 5 % type I error. We will use percentage and 95 % two-sided confidence interval to describe the qualitative endpoints, their change over time will be tested a McNemar test with a 5 % type I error.

The adverse events leading to a trial treatment discontinuation and the number of patients who discontinued the trial treatment, as well as the number and nature of grade 3 and 4 adverse events will be described.

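### No safety set is defined, and both defined analysis sets leave out treated patients who withdrew consent, so the tolerability percentages may lose adverse events that occurred before withdrawal

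*Combined protocol and SAP*

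**What the plan says.** Section 16.2.1 first sets the ITT population broadly: "All enrolled patients receiving at least one day of trial treatment will be included in the intent-to-treat (ITT) population". The next sentence narrows it: "Patients who withdrew their consent will be excluded in the ITT population". That exclusion carries no condition on how long the patient was treated or on what happened before withdrawal. The per-protocol set is then cut from ITT: "The per-protocol population will include all patients from the ITT population except those who did not fulfil the inclusion criteria" (a further exclusion for some treatment discontinuations follows). No safety or all-treated set is defined anywhere in the documents.

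Section 9.2 states the main tolerability endpoints as proportions of patients: "Percentage of patients with at least one serious adverse event as judged by DSMB as related to the trial treatment" (or to the trial strategy) and "Percentage of patients with grade 3 or grade 4 clinical and biological adverse events". The percentage of patients who interrupt trial treatment is listed in the same section, under biological efficacy. None of these names a denominator.

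Section 16.2.2 names ITT and per-protocol for the primary endpoint and ITT for changes in continuous endpoints. For categorical endpoints it says "We will use percentage and 95 % two-sided confidence interval to describe the qualitative endpoints", and for adverse events "as well as the number and nature of grade 3 and 4 adverse events will be described". Neither sentence names a population.

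On consent withdrawal, section 11.9.1 provides that the patient's "data will be removed (from the date of the consent's withdrawal) from the database". Section 11.9.2 treats giving up the trial as a separate category, and nothing in 16.2.1 removes those patients from ITT.

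**The concern.** A percentage of patients needs a denominator, and the plan offers only two. Both omit treated patients who later withdrew consent. An analyst who uses what is defined will take those patients out of the denominator and their earlier adverse events out of the numerator.

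This matters because the loss could be selective. Section 11.7 lists intolerance among the reasons for stopping treatment, so it could also lead a patient to leave the trial altogether. Section 11.2.1 lets a patient withdraw without giving a reason, and section 11.9.1 asks for a form and a date but not a reason; for giving up, section 11.9.2 does require the reason. A withdrawal driven by intolerance could therefore go unrecognised. Section 11.9.1 also allows withdrawn patients to be replaced, so the reported number of patients could reach target while some treated patients are missing from the harm rates.

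The trial has a single arm. There is no comparator in which a similar loss might offset this one, so the harm percentages are read at face value.

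**Working it through.** The plan gives no withdrawal rate and no expected adverse-event rate, so it has no figure of its own to reproduce here. The check has two parts: what the text implies, and how far a percentage could move.

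**Reading the sections together**

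1. ITT is treated patients minus consent withdrawals (16.2.1).
2. Per-protocol is a subset of ITT (16.2.1), so consent withdrawals are absent there too.
3. No third set is defined, and no sentence assigns the tolerability percentages to a set (9.2, 16.2.2).
4. Data are removed from the date of withdrawal (11.9.1). On its natural reading this leaves earlier adverse events in the database, so they could be counted.
5. Patients who give up or stop treatment are not removed from ITT by 16.2.1. The issue is confined to consent withdrawal.

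**Arithmetic**

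Let N be the patients treated, E those with at least one event, w the treated patients who withdrew consent, and k those of the w who had an event before withdrawing.

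- All treated patients: E/N.
- ITT as written: (E − k)/(N − w).

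The ITT figure is the lower one when N(E − k) < E(N − w), which reduces to k/w > E/N. So it falls only if withdrawn patients had events more often than the whole treated group, and it rises if they had them less often.

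Inputs: N = 160 is the planned sample size (section 16.1). E, w and k are assumptions. With E = 16, the all-treated rate is 16/160 = 10.0 %:

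| w | k | ITT as written | Result |
|---|---|---|---|
| 2 | 2 | 14/158 | 8.9 % |
| 2 | 0 | 16/158 | 10.1 % |
| 5 | 5 | 11/155 | 7.1 % |
| 5 | 2 | 14/155 | 9.0 % |
| 5 | 0 | 16/155 | 10.3 % |
| 8 | 8 | 8/152 | 5.3 % |
| 8 | 4 | 12/152 | 7.9 % |
| 8 | 0 | 16/152 | 10.5 % |

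Over assumed event rates of 5 %, 10 % and 20 % and w of 2, 5 or 8, the all-treated rate minus the ITT rate runs from +5.0 points to −1.05 points. The upper end is a 5 % rate with all eight events among eight withdrawals (8/160 = 5.0 % against 0/152 = 0 %). The lower end is a 20 % rate with eight event-free withdrawals (32/160 = 20.0 % against 32/152 = 21.05 %). With no withdrawals there is no difference.

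Appendix A8 reports 165 patients included. Using that number changes little: 16/165 = 9.7 % becomes 11/160 = 6.9 % if five withdrawals all had events, and 16/160 = 10.0 % if none did.

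**The case against.** The strongest reply is that this is an unspecified denominator, not a rule that discards adverse events. A reader might infer from 16.2.1 that the plan computes its tolerability percentages in ITT, so that these patients are certain to disappear from them. The documents do not say so. ITT is named for the continuous endpoints and for baseline description, and ITT with per-protocol for the primary endpoint; the categorical and adverse-event sentences name nothing. That part of the objection stands, and the point is therefore conditional on which set is used.

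A reader might also infer that the harm rates are biased downward. The documents do not support that either. The direction depends on whether withdrawn patients had more or fewer events than the rest, and nothing in the documents says which. The usual routes out for an intolerant patient, stopping treatment (with follow-up continuing to week 96 under 11.7) or giving up, keep the patient in ITT. This makes heavy enrichment of events among consent withdrawals less likely than in a trial with one exit category, though it does not rule it out.

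Third, safety oversight does not depend on ITT. Grade 3 or 4 events meet the SAE definition (13.1.3) and SAEs are notified to the sponsor within 24 hours (13.2.2). The DSMB reviews SAEs considered potentially related (7.1) and adverse events leading to discontinuation (14.2.3), and the annual safety report tabulates all SAEs (13.3.2). So the events remain visible to those bodies. These routes do not, however, produce the patient percentages in 9.2.

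Finally, section 16.2.3 promises a detailed analysis plan before any analysis. It may name a safety population, but it is not among the documents, and the definitions in 16.2.1 are what it would start from.

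**Conclusion.** The point holds in conditional form. The exclusion in 16.2.1 is explicit, it reaches both defined sets, and no set of all treated patients exists for the percentages in 9.2. If those percentages are computed in either defined set, adverse events before consent withdrawal are left out although 11.9.1 appears to keep them. Leaving the denominator open calls for the same correction.

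The size cannot be derived from the documents. Under the assumed 160 treated patients, 10.0 % rate and five withdrawals, the reported rate lies between 7.1 % and 10.3 %. The result rests on three things: that an analyst uses a defined set, that 11.9.1 keeps data from before the withdrawal date, and that some treated patients do withdraw consent. The point concerns the harm and treatment-interruption percentages only, not the scoring of efficacy.

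**What to change.** Add to section 16.2.1 a safety set: all patients who took at least one dose of trial treatment, including those who later withdrew consent, using their data up to the date of withdrawal. State in 16.2.2 that all adverse-event, SAE and treatment-interruption percentages are computed in this set. Report the number of treated patients who withdrew consent and the adverse events they had before withdrawing. It would also help to confirm in 11.9.1 that data recorded before the withdrawal date are retained.

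The cost is a few sentences and a changed denominator for these endpoints. No extra data collection is needed if 11.9.1 is read as above. The reported harm rates may come out slightly less favourable.

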16.2.2 Statistical methods

The primary endpoint is the virological success up to week 48 defined by the absence of 2 consecutive HIV-RNA plasma VL > 50 copies/mL within 2 to 4 weeks.

The therapeutic success is defined by the absence of virological failure and the absence of treatment interruption due to adverse event judged by DSMB as related to the trial treatment or procedure up to week 96.

In particular:

- Patients with 2 or more consecutive missing HIV-1 RNA plasma viral load values or lost to follow up will be considered as patients with treatment failure (failing patients).
- Patients who discontinue the treatment due to adverse event judged by DSMB as related to the trial treatment or procedure will be considered as failing patients.
- Patients who discontinued the treatment due to adverse event judged by DSMB as NOT related to the trial treatment or procedure will not be considered as failing patients.
- Patients who gave up will not be considered as failing patients.
- Patients who discontinued the trial treatment for any reason other than a virological failure or adverse event judged by DSMB as related to the trial treatment will not be considered as failing patients.
- Patients with a missing HIV-1 RNA value between 2 documented HIV-1 RNA plasma viral loads \leq 50 copies/mL will not be considered as failing patients.

Analysis of the primary endpoint will be performed on both ITT and per protocol populations. The 95% two-sided confidence interval of the percentage of patients in therapeutic success will be calculated and raltegravir/etravirine will be considered as an acceptable strategy if the lower bound is greater than 90%.

The changes in continuous endpoints will be compared in the ITT population (LOCF or other imputation method to be defined in the statistical analysis plan) using a two-sided non-parametric paired Wilcoxon test with a 5 % type I error. We will use percentage and 95 % two-sided confidence interval to describe the qualitative endpoints, their change over time will be tested a McNemar test with a 5 % type I error.

The adverse events leading to a trial treatment discontinuation and the number of patients who discontinued the trial treatment, as well as the number and nature of grade 3 and 4 adverse events will be described.

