9.1 Primary Endpoint

Proportion of patients remaining, at week 48, on virological success defined as the absence of 2 consecutive HIV-RNA plasma VL > 50 copies/mL within 2 to 4 weeks.

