16 STATISTICAL CONSIDERATIONS

16.1 Patients sample calculation

ANRS 163 ETRAL is a non-comparative phase II trial evaluating in HIV-1-infected patients, of at least 45 years of age, switching from a virologically suppressive boosted PI-containing regimen the capacity of a dual raltegravir/etravirine regimen to maintain the virological success as defined by the absence of 2 consecutive HIV-RNA plasma VL > 50 copies/mL within 2 to 4 weeks.

Raltegravir/etravirine will be considered acceptable if the percentage of patients in virological success at week 48 is significantly above 90 %.

Assuming a 95 % virological success rate, by including **160 individuals** and considering the strategy to be acceptable if no more than 8 individuals have virological failure; we will have a 95 % probability to discard a

combination for which efficacy is smaller than 90 % and we will select with a power of 80 % the strategy for which the efficacy is above or equal to 95 %.

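### Sections 16.1 and 16.2.2 contradict each other on the endpoint that decides acceptance: virological success at week 48 in one, therapeutic success in the other

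*Combined protocol and SAP*

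**What the plan says.** Section 9.1 gives the primary endpoint as "Proportion of patients remaining, at week 48, on virological success defined as the absence of 2 consecutive HIV-RNA plasma VL > 50 copies/mL", confirmed within 2 to 4 weeks. Section 16.2.2 opens consistently with this: "The primary endpoint is the virological success up to week 48 defined by the absence of 2 consecutive HIV-RNA plasma VL > 50 copies/mL".

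Section 16.1 attaches an acceptance rule to that endpoint: "Raltegravir/etravirine will be considered acceptable if the percentage of patients in virological success at week 48 is significantly above 90" per cent. The sizing follows from it. It assumes 95 % virological success and 160 patients, and accepts with at most 8 virological failures. The synopsis states the same cut-off as at least 152 successes. The claimed properties are a 95 % probability of discarding efficacy below 90 % and 80 % power at 95 %.

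Section 16.2.2 then defines therapeutic success as no virological failure together with "the absence of treatment interruption due to adverse event judged by DSMB as related to the trial treatment or procedure up to week 96". Section 9.2 lists it as a secondary endpoint, at both week 48 and week 96. A list of counting rules comes directly after the definition in 16.2.2. It covers consecutive missing viral loads, loss to follow-up, related and unrelated adverse-event stops, giving up, and an isolated missing value.

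The decision paragraph announces the analysis of the primary endpoint in the ITT and per-protocol populations. It continues: "The 95% two-sided confidence interval of the percentage of patients in therapeutic success will be calculated". The same sentence accepts the strategy when the lower limit of that interval exceeds 90 %.

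Section 16.2.3 promises a detailed SAP before any analysis; the documents do not contain one.

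**The concern.** Section 16.2.2 is where an analyst looks for the operative rule, and there the rule names a different endpoint from the one the trial was sized on. Read literally, it changes both the event (related adverse-event stops become failures) and the horizon (week 96 instead of week 48). An analyst following 9.1 and 16.1 and one following 16.2.2 would both comply with the protocol, yet could reach opposite conclusions.

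The counting rules deepen the problem. They sit under the definition of therapeutic success, and nothing says whether they also govern the primary endpoint. If they do not, virological success has no missing-data rule at all. The trial has a single accept-or-reject conclusion, and it depends on how these points are read.

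**Working it through.** **Inputs.** From 16.1 and the synopsis: n = 160, unacceptable rate 90 %, assumed virological success 95 %, accept with at most 8 failures. From 16.2.2: two-sided 95 % interval, lower bound above 90 %, interval method not named. Not given anywhere: an expected rate of therapeutic success, of related stops or of loss to follow-up.

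**Step 1: the plan's own figure.** With X the number of failures and q the failure probability, P(accept) = P(X ≤ 8) = Σ C(160,k) q^k (1−q)^(160−k), k = 0 to 8.
- q = 0.10: 0.017, so the 5 % error limit is met.
- q = 0.05: 0.593. The stated 80 % power is not reproduced by the stated cut-off, even on virological success. This is a separate defect.

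**Step 2: which endpoint does the interval rule fit?** At n = 160, a lower bound above 90 % allows at most 8 failures with Clopper-Pearson, Wilson, Agresti-Coull and Jeffreys intervals, and at most 9 with Wald. Four of the five methods therefore return the 152/160 cut-off that the synopsis and 16.1 state for virological success.

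**Step 3: can the verdicts differ?** Over the same period, therapeutic success cannot exceed virological success, because it adds a way to fail. The exact (Clopper-Pearson) lower bound is the 2.5 % quantile of Beta(x, n−x+1). The Wald bound is p − 1.96·√(p(1−p)/n). The patient counts below are illustrations.

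| Data in 160 patients | Endpoint | Successes | Exact | Wilson | Wald |
|---|---|---|---|---|---|
| 5 virological failures, 5 related stops | virological | 155 | 92.9 % | 92.9 % | 94.2 % |
| same | therapeutic | 150 | 88.8 % | 88.9 % | 89.999 % |
| 8 virological failures, 1 related stop | virological | 152 | 90.4 % | 90.4 % | 91.6 % |
| same | therapeutic | 151 | 89.6 % | 89.7 % | 90.8 % |

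The first data set is accepted on virological success and rejected on therapeutic success under all three intervals; with Wald the rejection is by a hair: 0.9375 − 1.96·√(0.9375·0.0625/160) = 0.9375 − 0.0375, just under 0.90. In the second, one patient reverses the verdict with the exact and Wilson intervals, but not with Wald.

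**Step 4: sensitivity under assumed rates.** Keep 5 % virological failure, add assumed percentage points of other failures, and apply the formula of step 1:

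| Added failures | 0 | 1 | 2 | 3 | 5 |
|---|---|---|---|---|---|
| P(at most 8 failures) | 59.3 % | 37.4 % | 20.5 % | 10.0 % | 1.7 % |

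This keeps virological failure at its week-48 design value. It does not model the extra failures that a week-96 horizon would bring.

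**Step 5: timing.** Section 7.4 plans 18 months of inclusion and the primary analysis at 30 months. The last patient reaches week 48 at about 18 + 11 = 29 months, and week 96 at about 18 + 22 = 40 months. A week-96 endpoint could not be complete at the planned primary analysis.

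**The case against.** The best defence is that this is a wording slip. Section 9.1, the synopsis, 16.1 and the first sentence of 16.2.2 all name virological success, the sentence just before the disputed one speaks of the primary endpoint, and steps 2 and 5 point the same way. That stands as evidence of intent. A reader might infer that the acceptance decision rests on therapeutic success alone. The documents do not support this, because 16.1 carries its own acceptance rule on virological success.

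A second defence is the promised SAP. If it was written before analysis and names one endpoint, it limits any choice after the results. It is not available here, so it cannot settle the matter. Equally, nothing in the documents shows that either endpoint was chosen with results in view.

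Third, the size of the effect rests on assumptions. No rate of related stops is given. The 18-patient pilot described in section 5.5.1 recorded no tolerability-related discontinuation, although 18 patients say little. The interval method is also open, and with Wald 151/160 would pass. The mechanism survives both points; a prediction of how often the verdicts would differ does not.

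**Conclusion.** The contradiction is certain from the text. The protocol contains two acceptance rules, one on a primary endpoint with a planned rate and cut-off, the other on a secondary composite with neither. They can disagree on identical data under every interval method tabulated, as 155/160 against 150/160 shows.

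The loss in the probability of acceptance, from 59.3 % to between 37.4 % and 1.7 %, holds only for the assumed 1 to 5 points of extra failures. It should be read as sensitivity, not as an expected loss. Nor should a reader conclude that correcting the endpoint restores the planned power: the starting value of 59.3 % already falls short of the stated 80 %, and this correction leaves it there.

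The point needs correction because the trial's one formal conclusion depends on it. Virological success up to week 48 is the better-supported reading.

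**What to change.** - In the decision sentence of 16.2.2, replace *therapeutic success* by *virological success up to week 48*, and name the interval method.
- Report therapeutic success at week 48 and week 96 as secondary, with a confidence interval and no acceptance threshold. Bring its horizon in 16.2.2 into line with 9.2.
- State for each counting rule whether it applies to virological success: two or more consecutive missing viral loads, loss to follow-up, giving up, isolated missing value. Keep the rule on related adverse-event stops for therapeutic success only.
- Appendix A8 of this version already reports first results and 165 included patients. Record which rule was fixed before analysis and on what date, and report the result under both endpoints.

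The cost is a few lines of text and no patients or data. Because results are already known, the change needs a dated justification. It may count as a substantial amendment under section 18.5 if it is judged to affect the scientific value of the trial.
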